6.1 Collection of Concomitant Medications

Investigators may prescribe concomitant medication or supportive care deemed necessary. All medications taken from 30 days prior to dosing through 90 days post discontinuation of SBRT should be documented in source records and in the CRF.

After 3 months post-SBRT, only medications used to treat respiratory disease or late radiation toxicities should be recorded through 12 Months post SBRT, including inhalers, steroids, oxygen supply, etc.

Additionally, any new anti-cancer therapy given in follow-up should be recorded in the CRF through 24-months post-SBRT or until disease progression.

Supportive care includes anti-emetic prophylaxis, hematopoietic growth factor used as ASCO guidelines, systemic antibiotics, hydration to prevent renal damage etc., consistent with local standard of practice.

6.2 Drug Interactions

In vitro, GC4711 is an inhibitor of CYP2D6. A clinical study of the potential of GC4711 to increase the concentration of drugs that are CYP2D6 substrates has not yet been conducted. Concomitant use of GC4711 may increase the concentration of drugs that are CYP2D6 substrates, which may increase the risk of toxicities of these drugs. Avoid concomitant use of GC4711 with CYP2D6 substrates where minimal increases in concentration of the CYP2D6 substrate may lead to serious or life-threatening toxicities (substrates with a narrow therapeutic range).

Such CYP2D6 substrates (see list below) include certain beta blockers, antidepressants, antipsychotics and antiarrhythmics.

In addition, concomitant use of GC4711 may decrease the concentration of active metabolites of prodrugs that require CYP2D6 for activation. Concomitant use of GC4711 with CYP2D6 prodrug substrates requiring functional CYP2D6 activity for their clinical benefit (e.g., codeine, tramadol, tamoxifen) may decrease their effectiveness.

Concomitant administration of a CYP2D6-substrate drug concurrent with administration of GC4711 should be limited to cases in which the treating investigator has determined that the use of the specific CYP2D6-substrate drug is medically necessary. In such cases, the patient should be carefully observed for clinical adverse events of the CYP2D6-substrate drug, the dose of which may require reduction.

Table 4 below provides some examples of CYP2D6-substrate drugs. See the GC4711 Investigator's Brochure for additional information.

Table 4 CYP2D6-substrate drugs

Beta Blockers:	Antidepressants:	Antipsychotics:	Others:
carvedilol	amitriptyline	haloperidol	aripiprazole
S-metoprolol	clomipramine	risperidone	atomoxetine
propafenone	desipramine	thioridazine	codeine dextromethorphan
timolol	duloxetine		doxepine
	fluoxetine		flecainide
	imipramine		mexiletine
	paroxetine		ondansetron
			oxycodone

			risperidone tamoxifen tramadol venlafaxine
--	--	--	---

6.3 Prohibited Medications

GC4711 may cause mechanism-related, transient hypotension, or lightheadedness. Because of the potential for such mechanism-related toxicities, the following drugs that could precipitate drops in blood pressure, should not be taken by patients while receiving GC4711/placebo:

- Nitrates (sublingual, oral or transdermal nitroglycerin; oral isosorbide mono- or dinitrate)
- Phosphodiesterase type 5 (PDE 5) inhibitors (sildenafil, tadalafil, vardenafil, avanafil).
- Alpha adrenergic blocking agents prescribed for hypertension, benign prostatic hypertrophy, prostate cancer treatment effects, and peripheral artery disease (doxazosin, prazosin, terazosin, tamsulosin, alfuzosin, silodosin, phenoxybenzamine, phentolamine).
- Other drugs that in the judgment of the treating investigator could create a risk of a precipitous decrease in blood pressure are prohibited until at least 24 hours after the last dose of GC4711 or placebo.
- Approved or investigational anti-cancer therapy (e.g., chemotherapy, immunotherapy, targeted therapy, hormone therapy, and biologic therapy) given before disease progression other than the protocol regimen without documentation of disease progression
- Any other investigational therapy not previously approved by the Sponsor

6.4 Toxicity Management and Infusion Modification

Anticipated toxicities of GC4711

Per the Investigator's Brochure, the following individual adverse events observed in healthy volunteer studies are listed and considered "expected" after GC4711 infusions:

- lightheadedness, faintness, or mild decrease in blood pressure
- mild facial tingling
- nausea
- headache
- pain, bruising, or redness at the spot where GC4711 was being given by IV
- pain or discomfort in the arm into which GC4711 was being given by IV
- fatigue

Toxicity Management/Infusion Modifications

Any subject who receives treatment on this protocol will be evaluable for toxicity. Each patient will be assessed for the development of toxicity according to the Schedule of Assessments (Table 1). Toxicity will be assessed according to the NCI Common Terminology Criteria for Adverse Events (CTCAE) Version 5.0.

Toxicities that will require infusion modification of the GC4711 or placebo administration include the following:

- Grade 2 or greater hypotension occurring within 1 hour of the end of GC4711 or placebo infusion
- Other Grade 3 or greater AEs judged by the investigator to be possibly attributable to the study infusion.

The dose of GC4711/placebo should not be reduced.

Patients who experience a toxicity noted above during or shortly after the infusion of GC4711/placebo should have their infusion times increased to 30 minutes.

If the toxicity recurs, the infusion time should be increased to 45 minutes, and may be increased to 60 minutes if hypotension occurs with a 45-minute infusion.

If toxicity occurs with a 60-minute infusion, the patient should be discontinued from further treatment with GC4711/placebo but should remain on study for all other protocol interventions (SBRT) /assessments.

Anticipated toxicities of SBRT

Explaining the risk of local high dose RT delivery is important for each individual subject. The following anticipated toxicities are used in the informed consent form based on Common Toxicity Criteria (CTCAE) version 5 (Table).

Very likely (80-90%):

- Fatigue (which generally goes away after the radiation therapy is completed)
- Abdominal pain, discomfort
- Nausea, loss of appetite

Less likely (30%):

- Temporary changes in blood work (decrease in blood counts, increase in liver enzymes), without symptoms
- vomiting (during therapy)
- diarrhea
- ulcers
- Skin irritation, redness, itchiness, discomfort
- Pain
- Breathing discomfort, hick-ups

Less likely, but serious (<20%):

- Gastric, esophagus, small bowel or large bowel irritation/ulceration, bleeding, fistula, obstruction, or changes in motility following therapy (may require medications or surgery, < 10% permanent changes)
- Radiation-induced liver disease (RILD, <5%). Classic RILD is a clinical diagnosis of anicteric ascites, hepatomegaly and elevation of alkaline phosphatase relative to other transaminases that may occur 2 weeks to 3 months following radiation to the liver
- Non-classic RILD includes elevation of liver enzymes and/or any decline in liver function within 12 weeks from start of therapy (~20%). RILD can lead to liver failure that could lead to death. There is an increased risk of liver toxicity in subjects with large tumors and/ pre-existing liver disease.
- Permanent thrombocytopenia (<1%); this may lead to bleeding
- Kidney injury (<1%); this may lead to changes on imaging and more rarely the need for medication.
- Spinal cord injury

Risk of rare but serious events is more prominent in subjects who did experience toxicities during chemotherapy or using co-medications for co-morbidity. Early signs of pain, obstruction and anemia need to be closely monitored and ulcers/bleeding treated with proton inhibitors or surgically if needed.

Table 5 Expected acute and late SBRT toxicities summarized

Acute:	Late:

• Abdominal pain• Nausea, vomiting• Diarrhea• Gastric/duodenal ulcers• Loss of appetite• Fatigue• Skin changes• Pain• Recurrent hick-ups• Renal/Liver dysfunction• Anemia, thrombopenia, neutropenia	
• Liver failure• Kidney failure• Abdominal bleeding• Bowel stenosis, obstruction, or perforation• Persisting thrombopenia, anemia• Spinal cord injury

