2 INTRODUCTION

2.1 Radiotherapy for Non-Small Cell Lung Cancer

Lung cancer is the leading cause of death in the United States, with approximately 135,000 deaths predicted in 2020 ([Ettinger 2020](#)). As recently as 2015, the 5-year survival rate for non-small cell lung cancer (NSCLC) was 25% ([Ettinger 2020](#)). While surgery for early-stage disease remains the preferred treatment, advances in noninvasive treatment modalities, such as targeted therapy, immunotherapy, and modified forms of radiotherapy (RT), have contributed to improved outcomes ([Ettinger 2020](#)). Stereotactic body radiotherapy (SBRT; also known as stereotactic ablative radiotherapy, or SABR) is an RT regimen that targets tumors with image-guided, short dose-intensive ablative courses of radiation, in contrast to conventionally fractionated RT ([Timmerman 2010](#)). SBRT is a current accepted alternative for surgery of peripheral lung lesions ([Stephans 2018, Timmerman 2010, Prezzano 2019](#)) and can be an alternative for larger or central tumors in a 5-fraction regimen in more fragile patients for whom chemo-radiation or surgery presents too great a risk of complications ([Peterson 2016, Bezjak 2019, Ettinger 2020](#)).

Modern RT techniques have enabled more precise delivery of high ablative doses with improved sparing of surrounding normal tissue. For early stage NSCLC, SBRT has become increasingly used as standard of care ([Timmerman 2018](#)). After initial demonstration of safety with SBRT for small peripheral NSCLC lesions, SBRT has been delivered to larger and more central lesions ([Bezjak 2019](#)), which identified SBRT dosing of 11.5 or 12 Gy x 5 fractions as associated with acceptable toxicity and with approximate 2-year rates for local control, overall survival, and progression-free survival of approximately 90%, 70%, and 55%, respectively. Use of SBRT for larger or centrally located NSCLC is reported to increase the risk of toxicity with a larger volume of normal tissue exposure ([Fakiris 2009, Woody 2015, Peterson 2016, Bezjak 2019](#)). SBRT can induce serious inflammatory reactions depending on dose and volume given to the lung and generate fibrosis and lung functional restrictions ([Lu 2018](#)). SBRT delivering a Biological Equivalent Dose of over 100 Gy to the lung is associated with grade 2 or worse pneumonitis in approximately 15% of patients ([Lu 2018](#)).

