Individual risk of radiation-induced pneumonitis depends on the volume of lung treated and the radiation dose administered, as well as patient characteristics and other treatment modalities used (immunotherapy itself has around 10% pneumonitis risk on its own ([Mohamad 2018](#))). The risk of clinical pneumonitis requiring medical intervention has been reported to be 9% to 28% after lung SBRT ([Kang 2015, Palma 2013, Yamashita 2014, Timmerman 2018](#)). Many more patients show radiological changes, which can often disturb response evaluation, as well as show milder changes which itself can limit retreatments for metastatic disease in the same lung ([Larici 2011, Kang 2015](#)). Significant (\geq grade 3) rates of pneumonitis have been reported varying from >10% to 21% ([Timmerman 2006, Baumann 2009, Stephans 2018](#)). Chemotherapy or/and immunotherapy carry their own pneumonitis risk and cumulative pneumonitis risk together with SBRT is observed and feared ([Zhao 2016, Mohamad 2018, Palma 2013](#)).

With improved systemic treatment, lung cancer patients are also living long enough to manifest late pulmonary toxicity after RT ([Larici 2011](#)). Moreover, in patients with recurrent disease, re-challenging RT also becomes technically possible. Based on nonclinical data, fibrosis obtained following the first SBRT treatment can significantly limit future treatment options. Due to their close relation to major airways, esophagus and major vessels, central tumors have a higher complication risk from radiotherapy, and are in general treated with 5 or more fractions of SBRT ([Lo 2009](#)) allowing normal tissue in the field more time to repair ([Timmerman 2006](#)).

In this trial, we target larger and/or central tumors associated with a higher pneumonitis and local failure risk, as well as a more fragile patient population. A sequential SBRT regimen of 5 fractions or 3 fractions for larger peripheral lesions delivering dose up till biologically equivalent (total) dose (BED) of 100Gy aligns with the standard dose for larger and/or central lesions ([Bejzak 2015](#), [Timmerman JAMA 2010](#)). The practice is shifting toward 5 fractions specifically for central localizations; however, for larger peripheral lesions, a 3-fraction regimen is still accepted.

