The RTOG 0813 trial identified SBRT dosing of 11.5 or 12 Gy x 5 fractions as associated with acceptable toxicity and with approximate 2-year rates for local control, overall survival, and progression-free survival of approximately 90%, 70%, and 55%, respectively ([Bezjak 2019](#)). Other studies ([Stone 2015](#), [Mohamad 2018](#)) reported control rates around 70% and PFS 50-60% at 2 years.

Radiation-induced lung injury is a slowly developing process, mostly manifesting as radiological changes only and transient symptoms around 4-6 months (mean 135 days) after treatment ([Jain 2018](#), [Ferrero 2015](#)). Clinically scored and symptomatic pneumonitis is seen in approximately 10% of patients 6 months after SBRT ([Kang 2015](#), [Yamashita 2014](#), [Mohamad 2018](#)). [Stone et al \(2015\)](#) referred to DLCO decline as the most objective measure of lung toxicity, referring to an observed decline (grade 1 or more) in 20-30% of patients. While a small decline is not seen as clinically significant, it is predictive for more severe accumulative toxicity risk in cases of pre-existing lung disease or in those with subsequent need for re-treatment in the thoracic area. Radiological changes in lung parenchyma are observed in over 40% of SBRT patients ([Kimura 2006](#), [Timmerman 2018](#)).

Approximately a 25% of patients experience declines in DLCO, reported after a 5-fraction regimen SBRT ([Stone 2015](#)). Slow decline in lung function and radiological changes are described after SABR/SBRT leaving a small portion of patients (mean 10%) with persistent significant decline at one year, which can be difficult to distinguish from recurrence ([Huang 2012](#)). Both lung function testing and radiographical changes are directly related clinical scoring at 3 months ([Tadasuke 2020](#)), explaining a gradual change from radiological to functional and finally clinical symptomatic SBRT complication related to dose and volume treated.

Both radiological and clinical data are needed to create future guidelines around lung SBRT ([Mohamad 2018](#), [Tadasuke 2020](#), [Palma 2013](#)). Complementary drugs such as GC4711 may add important value by increasing efficacy and reducing pneumonitis risk.

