4 STUDY DESIGN

4.1 Overall Design

GTI-4711-101 is a Phase I/II study of the safety of GC4711, and its potential to reduce radiation-related pulmonary injury, in combination with SBRT for clinical Stage I/II lymph node negative (T1 to T3N0M0) and/or central localized NSCLC.

After an open-label, Phase 1, safety run-in cohort of approximately 5 subjects has been completed, a randomized, placebo-controlled Phase 2 portion will be conducted.

Subjects must be referred for SBRT with peripheral lesions (>1-7 cm) or central localized (within an all direction, 2 cm- zone around the proximal bronchial tree, including ultra-central lesions, abutting the proximal bronchial tree or trachea) and node negative, non-metastatic NSCLC and have an Eastern Cooperative Oncology Group Performance Status (ECOG PS) score of 0-3 to be considered for enrollment (Buccheri 1996). Subjects with small peripheral lesions ($\leq 1\text{cm}$) are excluded, as we aim to improve outcome in larger, central NSCLC carrying a higher risk of pneumonitis and other RT related toxicities (including esophagitis, rib fractures, fistulae, stenosis, plexopathy, pericarditis, vascular events, etc. see Section 7.4), as well as local control failure. Feasibility of SBRT is judged by the treating physician. SBRT is planned on the tumor location for a dose of 10-12 Gy per 5 fractions, delivered on 5 sequential days or a dose of 18-20 Gy per 3 fractions (minimum of 18 and maximum of 96 hours between fractions for either regimen). All fractions should be given within 10 calendar days (+5 days in the case of a holiday or technical issue).

Phase 1: 5 subjects will each receive 100 mg of GC4711 by 15-minute IV infusion, before each SBRT fraction, beginning the day of the first fraction and ending the last day of SBRT (5 doses in total). SBRT is administered within 180 minutes (3 hours) of the end of the GC4711 infusion. All 5 SBRT doses should be given within 10 calendar days. All 5 subjects will be monitored for dose limiting toxicity (DLT) for 30 days post SBRT plus GC4711. DLT is defined in Section 7.5.

Safety will be judged unacceptable if 2 or more (i.e., no more than one) of the 5 subjects develop a DLT. Safety will be reviewed by a Safety Review Committee (SRC) consisting of the Medical Monitor, the Principal Investigator from each Phase 1 site, and additional designees by the Sponsor or the site Principal Investigators.

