4.7 Rationale for Study Design

In non-clinical development, GC4711 has shown the potential of increasing efficacy of high dose RT as well as limit associated inflammatory and fibrotic normal tissue reactions. As SBRT is a commonly used high dose RT treatment for early NSCLC, in this trial, we combine

GC4711/placebo with this national standard SBRT indication. Though SBRT has been shown to be effective in the treatment of small peripheral NSCLC (Timmerman 2010), its use for larger and/or central lesions has been associated with an increased risk of toxicity and less favorable local control (Stanic 2014, Bezzak 2015). By combining GC4711 with the 5-fraction regimen (Timmerman 2006, Lo 2010, Ettinger 2020), this study will assess both tolerability of the regimen and disease control. In addition to the routine efficacy parameters of local and regional control, control of distant metastatic rate, progression free survival (PFS) and overall survival (OS), we will also examine the effects of SBRT and GC4711 on response rate by the RECIST 1.1 criteria and degree of in-field tumor response.

Lung damage is the most common reported adverse effect and close monitoring of pneumonitis in this trial can be compared to extensive historical data (Timmerman 2006, 2010 and 2018). Radiation induced injury is a slow developing process, showing most radiological changes and symptoms around 3-6 months after treatment (Takeda 2013, Videtic 2013, Jain 2018, Ferrero 2015). Approximately 25% of patients treated with a 5-fraction regimen of SBRT encounter lung function decline (Stone 2015), of which a small portion (mean 10%) remain with a significant decline, which can be difficult to distinguish from recurrence (Huang 2012). Radiological changes have been described in larger number of subjects but are not always translated in clinical symptoms. Safety of GC4711 is the primary endpoint of the phase 1 portion and acute and late RT toxicities, as well as disease outcome are monitored as secondary endpoints in phase 2.

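### The SBRT risk list that Section 6.4 ties to the consent form is mainly abdominal and never names pneumonitis, in a lung radiotherapy trial

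*Combined protocol and SAP*

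**What the plan says.** Section 6.4, under the anticipated toxicities of SBRT, states: "The following anticipated toxicities are used in the informed consent form based on Common Toxicity Criteria (CTCAE) version 5". The list has three tiers.

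- **Very likely (80-90%):** fatigue, abdominal pain, and nausea with loss of appetite.
- **Less likely (30%):** seven items, including vomiting, diarrhea, ulcers, generic pain, and breathing discomfort grouped with hiccups.
- **Serious (<20%):** gastric, esophageal and bowel injury; classic radiation-induced liver disease (<5%); non-classic liver disease (about 20%); permanent thrombocytopenia (<1%); kidney injury (<1%); and spinal cord injury.

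The list adds: "There is an increased risk of liver toxicity in subjects with large tumors and/ pre-existing liver disease". Table 5 of Section 6.4 (not the laboratory table in Appendix 2 that carries the same number) summarizes expected toxicities. Its late effects include liver failure, kidney failure, abdominal bleeding and bowel perforation.

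Elsewhere the protocol describes a thoracic risk profile. Section 4.7: "Lung damage is the most common reported adverse effect and close monitoring of pneumonitis in this trial" can be set against historical data. Section 4.1 says the target population carries a "higher risk of pneumonitis and other RT related toxicities (including esophagitis, rib fractures, fistulae, stenosis, plexopathy, pericarditis, vascular events, etc". Section 2.1 gives rates: "Clinically scored and symptomatic pneumonitis is seen in approximately 10% of patients 6 months after SBRT"; a high biological dose to the lung "is associated with grade 2 or worse pneumonitis in approximately 15% of patients"; and "The risk of clinical pneumonitis requiring medical intervention has been reported to be 9% to 28% after lung SBRT".

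**The concern.** The list reads like text written for upper-abdominal SBRT. Here the target is a lung tumor, and inclusion criterion 5 admits central and ultra-central lesions. Yet the list omits by name the harm the protocol calls most common, and puts percentages on harms to organs for which it sets no dose limit. The remark that liver risk rises with large tumors is misleading in a trial that recruits large lung tumors.

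What is at stake is disclosure before consent, in both arms, since everyone receives SBRT. Appendix 1 says the sponsor or its designee supplies the consent template and must approve changes to it, so an error in the template could reach all of the up to 20 Phase 2 sites. Detection and grading of lung harm are not at stake: Sections 6.2, 7.1 and 7.4 cover dose limits, pneumonitis assessment, DLCO grading and late-toxicity collection.

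**Working it through.** The plan has no figure to reproduce on this point. The check compares content, then scales the omitted risk.

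**1. Composition of the two lists**

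- Section 6.4 list: 3 + 7 + 6 = 16 items. Gastrointestinal, hepatic or renal: abdominal pain; nausea and appetite; vomiting; diarrhea; ulcers; the gastric, esophageal and bowel item; classic liver disease; non-classic liver disease; kidney injury = 9 of 16. It is 10 if the blood-work item that mentions liver enzymes is counted.
- Table 5: 11 acute + 6 late = 17 entries. By the same rule, 6 of 11 acute and 4 of 6 late = 10 of 17.
- Pneumonitis, lung, fibrosis, rib, plexus or pericardium: named 0 times in either.

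**2. Coverage of the organ endpoints in Tables 2 and 3**

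| Endpoint with a dose limit | Section 6.4 list | Table 5 |
|---|---|---|
| Esophagitis | yes, inside a gastrointestinal item | no |
| Neuropathy (brachial plexus) | no | no |
| Pericarditis | no | no |
| Aneurysm | no | no |
| Impaired pulmonary toilet | no | no |
| Stenosis with atelectasis | no | no |
| Rib pain or fracture | generic pain only | generic pain only |
| Basic lung function | breathing discomfort only | no |
| Pneumonitis | no | no |
| Myelitis | yes | yes |
| **Clear matches** | **2 of 10** | **1 of 10** |

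Scored leniently, with generic pain counted as rib pain and breathing discomfort as one lung row, the list reaches 4 of 10 and Table 5 reaches 2 of 10. Pneumonitis is still not named.

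In the other direction, Tables 2 and 3 contain no liver, stomach, bowel or kidney limit. The late toxicities collected under Section 7.4 are respiratory and thoracic, esophageal, cardiac, cord or plexus, and vascular. None is hepatic, renal or intestinal.

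**3. Size of the omitted harm**

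Expected cases = 66 Phase 2 patients × the rate in Section 2.1:

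- symptomatic at 6 months, about 10%: 66 × 0.10 = 6.6, about 7
- grade 2 or worse, about 15%: 66 × 0.15 = 9.9, about 10
- needing medical intervention, 9% to 28%: 66 × 0.09 = 5.9 and 66 × 0.28 = 18.5, about 6 to 18
- grade 3 or higher, above 10% to 21%: 66 × 0.10 = 6.6 and 66 × 0.21 = 13.9, about 7 to 14

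These rates come from different sources and do not nest: the upper grade 3 figure exceeds the grade 2-or-worse figure. The top of the 9% to 28% range may be too high. One source cited for it is, by its title in Appendix 7, a meta-analysis of pneumonitis after chemoradiotherapy, and Section 7.1 says symptomatic incidence has fallen with modern technique. Even the 10% figure is at least ten times the <1% attached to kidney injury, which the list does name.

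**The case against.** The strongest reply is that the harm depends on a form that cannot be seen here. Section 6.4 says these toxicities are used in the consent form, not that nothing else is. Appendix 1 requires potential hazards to be explained in an IRB-approved form, and the IRB and investigators receive a protocol that describes thoracic risk repeatedly. This stands as a limit on the consequence: no one has been shown to be misinformed. It does not rescue the text. The general duty supplies none of the missing risks, and the list is the protocol's only statement of which SBRT toxicities the form uses. If the form is right, Section 6.4 misdescribes it.

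The second reply is that the 2 of 10 count is strict: breathing discomfort is reasonable lay wording for part of the pneumonitis picture, and the rib endpoint includes pain. That is fair, and the lenient score is shown. But breathing discomfort sits beside hiccups in a non-serious tier and disappears from Table 5. It does not convey a harm that can reach grade 3 or persist as lost lung function.

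Third, the case counts measure pneumonitis incidence, not faulty disclosure. That is correct, and they are used only to show that the unnamed risk is not a rare one.

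Fourth, some abdominal risk can be real when a field lies near the diaphragm; Section 6.2 allows wider margins for hemidiaphragm motion. That argues for restricting those items rather than deleting them outright.

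**Conclusion.** The concern holds. That the Section 6.4 list and Table 5 are mainly abdominal, omit pneumonitis by name and conflict with the rest of the protocol can be read directly from the text. The effect on participants is conditional: if the consent form carries this list and adds nothing, both arms are told of liver, bowel and kidney risks and not told by name of the protocol's most common SBRT harm. That harm would affect roughly 7 of 66 patients at the lowest symptomatic rate quoted for 6 months, with a wide range above that. These are patients who may develop pneumonitis, not patients known to have been misinformed. Because following the section as written would give the wrong organ risks, this is an error that needs correcting and not a matter of missing detail.

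**What to change.** Replace the Section 6.4 list and Table 5 with thoracic SBRT toxicities drawn from Sections 2.1, 4.1, 6.2 and 7.4: pneumonitis, fibrosis and lung-function decline; esophagitis; rib fracture; airway stenosis and fistula; plexopathy; pericarditis and other cardiac events; vascular events; cord injury. Attach the Section 2.1 pneumonitis rates, stating which grade and time point each refers to. Remove the abdominal items, or limit them to tumors whose field reaches the upper abdomen. Revise the monitoring advice after the list, which concerns obstruction, anemia and ulcers or bleeding, so that it covers lung symptoms.

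Then check the consent template against the corrected list. The cost is a text amendment and that check. IRB submission of a revised form and re-consent are needed only if the form carries the same list. Nothing changes in design, endpoints or sample size.

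A separate minor cleanup: Section 6.2, under the trachea and proximal bronchial tree, refers to excluding tumors within 2 cm of the bronchial tree. Inclusion criterion 5 admits exactly those tumors, so the clause should be deleted.
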